4.2 END OF STUDY DEFINITION

The end of the study is defined as completion of the last visit or procedure shown in the SoA in the trial globally.

5 STUDY POPULATION

5.1 INCLUSION CRITERIA

Candidates for this study must meet the following inclusion criteria in order to be enrolled in this trial:

- Patients must be 21 years of age
- Patients must require placement of a nasoenteral feeding tube
- Patients have an endotracheal tube, OR
 - Do not have an endotracheal tube but are sedated (RASS score of -2 or less) and/or obtunded (Glasgow Coma scale of9-12)
- Patients or legal authorized representative must be able to understand and adhere to all protocol procedures and be willing and able to provide written informed consent

5.2 EXCLUSION CRITERIA

Candidates for this study must not meet any of the following exclusionary criteria in order to be enrolled in this trial.

- Patients must not have a history of:
 - Esophageal varices or ulcers
 - Upper airway obstruction
 - Upper GI stenosis or obstruction
 - Trauma involving sinuses, nares face or neck that would prevent NG tube insertion
 - Deformities of the sinus cavities and/or skull base
 - Esophageal cancer or neoplasm
- Patients must not have a significant concomitant illness that would adversely affect their participation in the study
- Female patients who are pregnant or lactating

5.3 FEMALE PATIENTS WHO ARE PREGNANT OR LACTATING

A urine pregnancy test will be required to rule out pregnancy in females of child-bearing potential. For female patients with a Foley catheter, urine samples for the pregnancy test are to be taken from the sample port on the catheter.

5.4 SCREEN FAILURES

Screen failures are defined as participants who consent to participate in the clinical trial but are not subsequently entered in the study and do not complete the Procedure Visit. A minimal set of screen failure information is required to ensure transparent reporting of screen failure participants, to meet the Consolidated Standards of Reporting Trials (CONSORT) publishing requirements and to respond to queries from regulatory authorities. Minimal information includes demography, screen failure details, eligibility criteria, and any serious adverse event (SAE).

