2.3 RISK/BENEFIT ASSESSMENT

2.3.1 KNOWN POTENTIAL RISKS

Risks associated with the placement and use of nasoenteral tubes include the following:

- Placement in the lungs resulting in:
 - o pneumothorax
 - pneumonia and sepsis
- Irritation and coughing during placement
- Damage to nasal ciliary epithelium leading to infection and/or sinusitis following long-term presence of an nasoenteral tube
- Perforation of the esophagus in patients with esophageal varicies, ulcers, or history of cancer or neoplasms
- Perforation of the base of the skull in patients with deformities of the skull base and/or sinus cavity
- Reflux of stomach contents into the esophagus leading to aspiration
- Parotitis
- Minor bleeding during tube placement

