8.2.4 TIME PERIOD AND FREQUENCY FOR EVENT ASSESSMENT AND FOLLOW-UP

The occurrence of an adverse event (AE) or serious adverse event (SAE) may come to the attention of study personnel during study visits and interviews of a study participant or upon review by a study monitor.

AEs not meeting the criteria for SAEs will be captured on the appropriate case report form (CRF). Information to be collected includes event description, time of onset, clinician's assessment of severity, relationship to NUTRIPLACE System, and time of resolution/stabilization of the event. All AEs occurring while on study must be documented appropriately regardless of relationship. All SAEs determined to be related to the NUTRIPLACE System will be followed to adequate resolution or stabilization.

Any medical condition that is present at the time that the participant is screened will be considered as baseline and not reported as an AE. However, if the study participant's condition deteriorates at any time during the study, it will be recorded as an AE.

Changes in the severity of an AE will be documented to allow an assessment of the duration of the event at each level of severity to be performed. AEs characterized as intermittent require documentation of onset and duration of each episode.

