9.2 SAMPLE SIZE DETERMINATION

This feasibility trial will include fifty (50) patients completing the Procedure Visit (NasoEnteral Tube placement) and five operators. Each operator must complete training on one run-in subject prior to participating in this study. Patients or patients' LAR who chose not to participate after informed consent but prior to procedure, and patients who because of system malfunction or because of undiscovered or unreported physical reasons (e.g. deteriorating health, anatomical anomalies, mechanical obstruction, etc.) cannot complete the Procedure Visit (NasoEnteral Tube placement) will be considered Screen Failures, not be considered in the total patient count, but will be reported in the ITT dataset as defined below. If less than 45 patients will complete the Follow-up Visit (confirmation of tube tip anatomical location), an enrollment of another 5 patients will be considered.

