9.3 POPULATIONS FOR ANALYSES

Populations that will be analyzed include the following:

- Intention-to-Treat (ITT) Analysis Dataset (i.e., all enrolled participants)
- Per-Protocol Analysis Dataset: defines enrolled patients for whom no protocol deviations were noted
- Full Cohort Dataset: includes the ITT population plus the Run-in patients

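### Sections 9.2 and 5.4 allow an SAE-only minimum dataset after an abandoned insertion, other sections require all AEs, and nothing says which rule governs

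*Combined protocol and SAP*

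**What the plan says.** Section 9.2 removes certain patients from the count of 50. Besides those who decline after consent but before the procedure, it names "patients who because of system malfunction or because of undiscovered or unreported physical reasons", with anatomical anomaly, mechanical obstruction and deteriorating health as examples. Those who for such a reason "cannot complete the Procedure Visit (NasoEnteral Tube placement) will be considered Screen Failures, not be considered in the total patient count". The same sentence adds "but will be reported in the ITT dataset as defined below", and Section 9.3 defines that set as "Intention-to-Treat (ITT) Analysis Dataset (i.e., all enrolled participants".

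Section 5.4 sets the data requirement for screen failures: "Minimal information includes demography, screen failure details, eligibility criteria, and any serious adverse event (SAE". Its own definition covers people who consent "but are not subsequently entered in the study and do not complete the Procedure Visit".

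The general AE rule is in Section 8.2.4: "All AEs occurring while on study must be documented appropriately regardless of relationship". That section also sends non-serious events to the CRF, and Section 8.2.5 gives 48 hours to report them. Section 7.1 asks for all data up to discontinuation, with the reason. The Synopsis treats the patient as enrolled at the procedure visit, and Table 1 in Section 1.3 schedules AE assessment at both the procedure and the follow-up visit.

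**The concern.** An undiscovered obstruction or anomaly may come to light only as the tube is advanced, and the System may malfunction during use. The screen-failure label in Section 9.2 can therefore reach patients already exposed to the device. The minimum dataset in Section 5.4 suits people who were never treated. For an exposed patient it leaves out non-serious AEs, the guidance-relatedness category of Section 8.2.3.2 and the number of attempts.

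The study's one objective is safety. Section 2.3.1 lists placement harms that can well be non-serious, such as "Minor bleeding during tube placement" and coughing. If a site applied the minimum to abandoned insertions, such events would not reach the AE tables. Nor would they reach the Clinical Events Committee, which under Section 10.1.5 adjudicates device involvement in any AE but can only work on what is reported.

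**Working it through.** The plan has no figure to reproduce: the Synopsis says the 50 has no statistical basis, and Section 9.1 states no hypothesis. The check is a comparison of rules, followed by an illustration.

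**Rules for a patient whose insertion was started and then abandoned for a reason listed in Section 9.2**

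1. *Status.* Section 9.2 says screen failure. The Synopsis says enrolled, since enrolment does not depend on completing the placement. Section 9.2 itself, with 9.3, puts the patient in ITT. The definition in Section 5.4 joins two conditions, not entered and visit not completed. An enrolled patient meets the second but not clearly the first.
2. *AE collection.* Section 5.4 lists SAEs only, as a minimum. Section 8.2.4 requires all AEs, but for patients on study. Whether it applies depends on step 1, which is unresolved.
3. *Assessment after the attempt.* Section 7.1 reaches only to discontinuation. AE assessment at 20-48 hours is tied to the follow-up visit, which Section 9.2 describes as confirming where the tube tip lies. After an abandoned attempt there may be no tube to locate, and no section says the visit still takes place.
4. *Effect on the primary endpoint.* Success requires correct position and no guidance-related AE. An abandoned placement already fails on position, so if it is counted in ITT as a failure, an unrecorded AE leaves procedure success unchanged. Only the AE tabulation can move.

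**Illustration**

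Inputs: 50 completers (Section 9.2). Assumptions, not in the documents: no AE of the type tabulated among completers; k abandoned insertions, with k = 5 as the main case and 1 and 10 as the range; m non-serious events (one per patient) missed among the k.

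The rate is m/(50 + k). The exact (Clopper-Pearson) 95% limits for x events in n are the 0.025 quantile of Beta(x, n - x + 1) and the 0.975 quantile of Beta(x + 1, n - x). For x = 0 the lower limit is 0 and the upper is 1 - 0.025^(1/n).

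What would be reported under the SAE-only minimum:
- Completers only: 0/50, upper limit 1 - 0.025^(1/50) = 7.1%.
- With 5 abandoned insertions in the denominator: 0/55, upper limit 1 - 0.025^(1/55) = 6.5%.

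What full recording would show:

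| k | m | Rate | Exact 95% CI |
|---|---|---|---|
| 1 | 1 | 1/51 = 2.0% | 0.05-10.4% |
| 5 | 1 | 1/55 = 1.8% | 0.05-9.7% |
| 5 | 3 | 3/55 = 5.5% | 1.1-15.1% |
| 5 | 5 | 5/55 = 9.1% | 3.0-20.0% |
| 10 | 1 | 1/60 = 1.7% | 0.04-8.9% |
| 10 | 10 | 10/60 = 16.7% | 8.3-28.5% |

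Adding the abandoned cases to the denominator without their non-serious events makes the result look slightly better (upper limit 6.5% instead of 7.1%). ITT membership alone therefore does not cure the problem.

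**The case against.** The strongest reply is that the plan already requires what is asked. The list in Section 5.4 is a floor, and no section tells a site to leave out non-serious events. A patient with a tube being advanced is enrolled and in ITT, so Sections 8.2.4, 8.2.5 and 7.1 and the AE assessment in the procedure step all apply. Much of this stands. A reader might infer that non-serious events after abandoned insertions are definitely not collected. The documents do not support that. But the general rule binds only for patients on study, while the screen-failure label belongs to a section about people not entered in it. A site could reasonably follow either.

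A second reply is that the primary endpoint is safe, because an abandoned placement fails it anyway. That stands, provided such placements are counted as failures in ITT. A reader might infer that procedure success is inflated by the missing AEs, and that inference fails.

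A third is that nothing shows abandoned insertions to be common or especially harmful. That also stands. Section 9.2 covers refusal before the procedure and deteriorating health, and a malfunction may appear during setup. It is tempting to call these the placements where guidance-related harm is most likely, but no section says so. Under Section 8.2.3.2, an injury caused by an anatomical obstruction may be judged not likely related to the guidance system.

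**Conclusion.** The protocol is inconsistent on AE collection after an abandoned insertion. The consequence is a possible understatement of the AE tabulation among device-exposed patients, and a gap in securing their 20-48 hour assessment. It is not an established loss of data. The conclusion rests on two readings: that the reasons listed in Section 9.2 can arise after insertion begins, and that a site might treat the Section 5.4 minimum as sufficient.

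The size cannot be derived from the documents. In the main illustration a reported rate of zero would become 1.8% to 9.1%; the number of abandoned insertions and their event rate are both assumed. With no hypothesis to test, no formal decision depends on the figure, but the AE table is central to a study whose sole objective is safety. The inconsistency should be corrected.

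**What to change.** Reconcile Sections 5.4 and 9.2 with 8.2.4. Section 9.2 must be amended too, because the label on uncompleted placements originates there.

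- In 5.4 and 9.2, limit the screen-failure label and the minimal dataset to patients in whom insertion never started.
- State that for any patient in whom tube insertion with the System was attempted, all AEs (serious and non-serious), the guidance-relatedness category and the number of attempts are recorded through the existing 20-48 hour follow-up window, whether or not placement was completed.
- In 9.3 and 9.4, tabulate AEs on all patients with an attempted insertion.

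Whether such patients count toward the 50 is a separate matter, which this change need not settle. The cost is wording and a few more of the existing CRF pages for in-patients. The reported AE rate may come out slightly higher.

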5.5 STRATEGIES FOR RECRUITMENT AND RETENTION

Subjects for this trial will be recruited from the currently hospitalized and require placement of an NET tube. It is anticipated that two months will be required to treat the run-in patients and enroll the full trial cohort. Given the acute, in-hospital nature of this trial, no special measures will be needed to retain enrolled patients.

A full description of the System and its use is provided in the Investigator's Brochure (Attachment 1) the NUTRIPLACE System User Manual and the NasoEnteral Tube Instructions for Use (Attachment 2). The NUTRIPLACE System will be used on enrolled subjects following the documented methods and in consideration for the investigational sites standard of care regarding the placement of nasoenteral feeding tubes.

The study of the NUTRIPLACE System is considered a non-significant risk study of an investigational medical device. The rationale supporting the non-significant risk status is included in the NSR Letter (Attachment 3).

6.2 PREPARATION/HANDLING/STORAGE/ACCOUNTABILITY

6.2.1 ACQUISITION AND ACCOUNTABILITY

Sufficient supplies of the NUTRIPLACE System will be provided to the investigational site directly by manufacturer, Nutriseal L.P.

6.2.2 PRODUCT STORAGE AND STABILITY

The NUTRIPLACE System does not require special storage conditions, e.g., it may be stored at room temperature. The Nutriseal NasoEnteral Tube should be stored in a clean dry location. The shelf life for the product is stable for a minimum of 6 months.

It is expected that the investigational site will store all components of the system in a secure location between uses.

6.2.3 PREPARATION AND USE

Preparation and use of the NUTRIPLACE System are discussed in detail in the NUTRIPLACE System User manual and the NasoEnteral Tube Instructions for Use (Attachment 2).

6.3 MEASURES TO MINIMIZE BIAS: RANDOMIZATION AND BLINDING

This is an open label, non-randomized feasibility trial with limited bias expected. Bias in this study will be controlled through use of an independent CEC that will review and assess relatedness of reported adverse events to the NUTRIPLACE System.

6.4 CONCOMITANT THERAPY

For this protocol, a prescription medication is defined as a medication that can be prescribed only by a properly authorized/licensed clinician. Medications to be reported in the Case Report Form (CRF) are concomitant prescription medications limited to sedatives/any medication with sedative effect, anticoagulants and prokinetic agents.

7 STUDY INTERVENTION DISCONTINUATION AND PARTICIPANT DISCONTINUATION/WITHDRAWAL

7.1 PARTICIPANT DISCONTINUATION/WITHDRAWAL FROM THE STUDY

In the event a patient is discontinued from this study for any reason, all data will be collected through the time of discontinuation as well as the reason for discontinuation.

7.2 LOST TO FOLLOW-UP

Given the acute, in hospital nature of this trial, follow-up loss of patients is not expected.

8 STUDY ASSESSMENTS AND PROCEDURES

8.1 EFFICACY ASSESSMENTS

The following assessments will contribute to assessment of the NUTRIPLACE System:

- Targeted Physical examination: height, weight
- Vital signs: pulse, respiration, blood pressure, and oxygen saturation via pulse oximetry (Sp02)
- Radiographic assessments: Abdominal and/or thoracic X-Ray will be required following the
 placement of the Nutriseal NasoEnteral Tube to confirm placement location and once during the
 follow-up period.
- Number of Placement Attempts per Patient:
 - **Replacement** is defined as complete removal of the tube from the patient or retraction above the level of the pharynx followed by reinsertion

- *Repositioning* is defined as changing position of tube without complete removal of the tube
- **Tube Migration:** Retrograde migration from desired placement position
- Assessment of adverse events

The specific timing of data collection is defined in section 1.3, Schedule of Activities.

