1.2 SCHEMA

Figure 1: Study Flow Chart

Screening

- Obtain informed consent
- •Assess inclusion/exclusion criteria
- •Capture baseline demographics, medical history and concomitant medications
- Collect clinical assessments (height, weight, previous X-Ray interpetation if available)

Enrollment

- •Affirmation of informed consent and enrollment (Only if screening visit is independent of procedure visit)
- •One run-in subject per operator
- •Enroll Fifty (50) Patients

Procedure (within 2-days of screening)

- •Collect pre-procedure vital signs
- Place NasoEnteral Tube using NUTRIPLACE System
- Collect procedure information (including number of tube replacement events)
- •Confirm placement via X-Ray (within 5 hours)
- •Assess for adverse events and device related side effects

Follow-up (20-48 hours post procedure)

- Collect vital signs
- •Confirm tube location using NUTRIPLACE System and X-Ray
- •Collect information regarding tube migration and reposition
- •Assess for adverse events or device related side effects

Study Exit

SCHEDULE OF ACTIVITIES (SOA) 1.3

The study schedule for this evaluation is presented below in **Table 1**.

Table 1: Study Schedule

Procedures, Evaluations and	Study Visits			
Tests	Screening	Procedure (Within 2 days of Screening Visit)	Follow-up (20-48 hours after Procedure Visit)	
Informed Consent	Х	X ³		
Inclusion/Exclusion Criteria	Х			
Demographics	Х			
Medical History (Acute and Past)	Х			
Concomitant Medications ⁴	Х			
Examinations				
Targeted Physical Exam	Х			
Vital Signs		Х	Х	
Nutriseal [™] nasoenteral tube		v		
Placement		^		
Confirm Anatomical Location				
NUTRIPLACE System			v	
Abdominal and/ or thoracic X-		Y ⁶	X	
ray⁵		^	^	
Adverse Events		Х	Х	

³ Affirmation of informed consent is only required if procedure visit is independent of screening visit.

 ⁴ Limited to sedatives/any medication with sedative effect, anticoagulants and prokinetic agents.
 ⁵ Additional X-Rays may be taken if clinically indicated.

⁶ Within five hours of placement.

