2.2 BACKGROUND

Enteral nutrition is the preferred route for the provision of nutritional support in most critical ill patients with functional gastrointestinal tract. The nasoenteric tube (NET) are easily placed at the bedside. Patients that most commonly require a NET are in the surgical, intensive care, neonatal and pediatric settings^{1,2}. Enteral tube feeding is thought to preserve the integrity of the gut mucosa, and to reduce infectious complications. Achieving early enteral nutrition (EN) in critically ill patients is associated with fewer major complications, reduced mortality and length of hospital stay, and significant cost savings^{3,4,5,6,7}.

It is estimated that approximately 1.2 million feeding tubes are placed blindly each year in the United States alone^{2,8,9,10,11}. Despite the obvious advantages of the enteral tube feeding, inadvertent placement of NET into the airway is relatively common and can result in significant pulmonary injury including pneumothorax and pneumonia. Airway misplacement occurs in 1.2–4 % of blind NET insertions, with 0.2 to 1.2% of all the feeding tube placements cause pulmonary complications to patients^{3,12,13,14,15,9}.

The gold standard for detecting inadvertent placement of a feeding tube in the lungs is radiography. However, because of its cost, possible delay of feedings while waiting for radiography, and risk for radiation exposure, clinicians continue to seek for alternative methods to confirm correct placement^{3,16}.

All the above mentioned, emphasizes the fact that safe and effective delivery of nasoenteral tube feedings requires assurance that the feeding tube tip is in a proper position¹⁷.

The NUTRIPLACE System is an electromagnetic tracking system which tracks the path of the feeding tube during placement. The System utilizes an ElectroMagnetic (EM) sensor in the NET's distal tip and a field generator as well as plate sensor (patient angle) and reference sensor (provides horizontal scaling of the body contour of the patient) and a Stylus which marks two anatomical landmarks (Xiphoid Process and Suprasternal Notch).

The benefit of the system when NET is misdirected into the pulmonary system is a real-time visual tracing, which may prompt users to withdraw the tube and reinsert it.

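### The required film need not show the chest and no baseline film is scheduled, so silent or small lung injuries may go unseen or be undatable, to an extent the documents do not let us size

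*Combined protocol and SAP*

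**What the plan says.** Section 8.1 states "Abdominal and/or thoracic X-Ray will be required following the" placement of the tube, "to confirm placement location and once during the" follow-up period. The purpose given is tube location; looking for lung injury is not mentioned. Table 1 (section 1.3) repeats the choice, "Abdominal and/ or thoracic X"-ray, at the Procedure and Follow-up visits. A footnote times the first film: "Within five hours of placement". Another footnote leaves further films optional: "Additional X-Rays may be taken if clinically indicated".

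No film is marked at Screening. The schema in section 1.2 lists among the screening items only "previous X-Ray interpetation if available".

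Section 2.3.1 opens its list of risks with "Placement in the lungs resulting in" pneumothorax, or pneumonia and sepsis. Section 2.2 says "The gold standard for detecting inadvertent placement of a feeding tube in the lungs is radiography". The primary endpoint (section 3) needs both a correct tube position and no adverse event attributed to the guidance. Section 8.2.4 treats a condition already present at screening as baseline rather than as an adverse event.

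**The concern.** Section 2.2 describes the device's benefit as showing the operator that the tube has gone toward the lungs, so that it can be pulled back and reinserted. An airway pass that is corrected and ends in the stomach is thus a course of events the protocol itself foresees. A film limited to the abdomen would show a well-placed tip and need not show whether the lung was injured on the way.

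Such an injury could be hard to notice otherwise. Under section 5.1 the patients are intubated, sedated or obtunded, so they can report little, and their respiratory signs may have other causes. If a lung finding does appear, its timing matters: section 8.2.4 makes it either baseline or an adverse event, and no baseline chest image is required to settle which. Section 5.2 does not exclude a recent failed placement, so a pre-existing injury from an earlier tube is possible.

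At stake is what a statement of no guidance-related events can support. It means less for patients whose chest was never imaged, and the plan does not identify them.

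**Working it through.** **No plan figure to reproduce.** Section 9.1 states no hypothesis, and the synopsis says the sample size is not statistically based. The calculations below only gauge how much one event matters.

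**Inputs from the documents.** 50 patients completing the Procedure Visit (section 9.2). Pulmonary complications in 0.2 to 1.2% of feeding tube placements and airway misplacement in 1.2 to 4% of blind insertions (section 2.2).

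**Input not in the documents.** The share *s* of lung injuries that would be detected. It is an assumption, shown as a range.

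**Step 1: expected pulmonary complications.** 50 × 0.002 = 0.1 and 50 × 0.012 = 0.6.

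**Step 2: chance of at least one detected event**, 1 − (1 − p·s)^50:

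| Assumed s | p = 0.2% | p = 1.2% |
|---|---|---|
| 100% | 9.5% | 45.3% |
| 75% | 7.2% | 36.4% |
| 50% | 4.9% | 26.0% |
| 25% | 2.5% | 14.0% |

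**Step 3: what zero observed events would rule out.** With full detection the one-sided 95% upper bound is 1 − 0.05^(1/50) = 5.8%. With detection share *s* the bound on the true rate is that figure divided by *s*: 7.8% at 75%, 11.6% at 50%, 23.3% at 25%.

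**Step 4: weight of one event on the primary endpoint.** Exact two-sided 95% intervals: 50/50 = 100% (92.9 to 100); 49/50 = 98% (89.4 to 99.9). This contrast applies only if the event is judged guidance-related.

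**Step 5: airway misplacement, for context.** 50 × 0.012 = 0.6 and 50 × 0.04 = 2.0. These are misplacements, not injuries, and the rate is for blind insertion, whereas this device is guided. They indicate how often the corrected-pass scenario might arise without guidance. They do not count harms that a film could miss.

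**Reading the sections together.** Section 8.1 and Table 1 agree that an abdominal-only film suffices. Section 8.2.4 needs to know what was present at screening; the schema supplies imaging on that only when it happens to exist. Section 6.3 relies on the Clinical Events Committee (CEC) to control bias, but its task is to judge adverse events that have been reported.

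**The case against.** The strongest case against is that the film has a different job. It confirms tube location; adverse events are found clinically. Pulse, respiration, blood pressure and SpO2 are taken at both study visits, adverse events are assessed at both, extra films can be taken when indicated, and section 8.2.4 requires every on-study event to be documented whatever its cause. Section 8.1 also defines retraction above the pharynx with reinsertion as a replacement, and the schema collects the number of these, so some corrected passes leave a record. All of this stands. It narrows the point to injuries that are silent or small, and to signs with competing explanations.

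The numbers also have limits. Only events judged guidance-related fail the endpoint, so 0.1 to 0.6 overstates the expected failures from this source at the cited rate. Zero is the most likely count even with perfect imaging: the complements of the first row of Step 2 are 90.5% and 54.7%. The User Manual, the Instructions for Use, site practice or the CRF, none of which is available here, may already specify the imaging field.

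A reader might infer that a finding of no guidance-related event simply means nobody looked, or that pneumothorax would generally be missed. The documents do not support either, given the clinical detection above. A reader might also see an error in the amendment log, which justifies dropping the recent-failed-placement exclusion by appeal to a chest X-ray that the current text does not require. The log explains superseded wording, and a mismatch with it is not in itself a fault. The point rests on sections 1.2, 1.3, 5.2, 8.1 and 8.2.4.

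What survives is that the CEC cannot assess an injury that was never imaged or reported, and may lack a baseline for one that was.

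**Conclusion.** The point holds in a limited form. It is certain that the wording accepts films without the chest at both visits and that no baseline film is scheduled. It follows that some lung injuries may be missed, or may not be assignable to before or after the study device.

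The size of any under-detection cannot be computed: the documents give neither the frequency of abdominal-only films nor a detection rate by film type. The table in Step 2 and the bounds below 100% detection in Step 3 are illustrations resting on an assumed *s* and on the cited rates applying to this guided device. With fewer than one pulmonary complication expected in 50 patients at those rates, one missed or misattributed event could change the safety summary. That justifies a reporting change. It does not show that the endpoint is invalid, and no sample size figure is affected.

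**What to change.** 1. In section 8.1 and Table 1, state that the film already required should include the chest where the same exposure allows. Mandate no added exposure and no new baseline film.
2. Add three CRF items: the field imaged, any recent failed placement, and whether a pre-procedure chest film exists. Give these to the CEC with each event it reviews.
3. In section 9.4, keep the primary endpoint as defined. Report how many patients had no chest field imaged, labelled as lung injury not radiographically assessed, and show procedure success with and without them.

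The cost is three CRF items and one sensitivity table. The assessed denominator may be smaller or the result less favourable. For illustration, if half of the 50 patients had no chest field (an assumption), 25 successes in 25 would give an exact two-sided 95% lower limit of 0.025^(1/25) = 86.3%, against 0.025^(1/50) = 92.9% for 50 in 50. Because no baseline film is required, attribution stays uncertain for patients without a prior chest film. The change makes that visible but does not remove it.
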